Table JAIA.6.4. Description and Derivation of Efficacy/Health Outcomes Measures and Endpoints	29
Table JAIA.6.5. Datapoint Sets for Use in Efficacy/Health Outcomes Analyses	40
Table JAIA.6.6. Description of Efficacy/Health Outcomes Analyses	41
Table JAIA.6.7. Summary Tables Related to Adverse Events	51
Table JAIA.6.8. Summary Tables Related to Clinical Laboratory Evaluation	52
Table JAIA.6.9. Parameter Definitions Related to Vital Signs	52
Table JAIA.6.10. Summary Tables Related to Vital Signs	53
Table JAIA.6.11. Summary Tables Relate to Hepatic Safety	53
Table JAIA.6.12. Summary Tables Related to Hematologic Changes	54
Table JAIA.6.13. Summary Tables Related to Lipid Effects	55
Table JAIA.6.14. Summary Tables Related to Effects on Renal Function	55
Table JAIA.6.15. Summary Tables Related to Effects on CPK	56
Table JAIA.6.16. Summary Tables Related to Infections	57
Table JAIA.6.17. Summary Tables Related to Allergic Reactions/Hypersensitivities	58
Table JAIA.6.18. Summary Tables Related to MACE and Other Cardiovascular Events	59
Table JAIA.6.19. Summary Tables Related to VTEs	59
Table JAIA.6.20. Summary Tables Related to ATEs	59
Table JAIA.6.21. Summary Tables Related to Malignancies	60
Table JAIA.6.22. Summary Tables Related to Gastrointestinal Perforations	60
Table JAIA.6.23. Summaries Related to Depression and Suicide	61

List of Figures

Figure		Page
Figure JAIA.5.1. Illustrates the study design.....		13
Figure JAIA.6.1. Illustration of graphical multiple testing procedure with initial α allocation and weights.		23

List of Appendices

Appendix		Page
Appendix 1.	Selection of Medications.....	68
Appendix 2.	Summary Tables Related to Patient Characteristics.....	73
Appendix 3.	Efficacy Laboratory Analytes	77
Appendix 4.	Joint Assessment	78
Appendix 5.	Time to First Severe Flare.....	79

3 Revision History

Statistical Analysis Plan (SAP) Version 1 was approved prior to unblinding.

Statistical Analysis Plan Version 2 was approved prior to the primary outcome database lock and included the following key changes:

- Added clarification on summarization of patients randomized to 4 mg with decreased renal function at screening.
- Added clarifications for the time to first severe Systemic Lupus Erythematosus Disease Activity Index (SLEDAI) Flare Index (SFI) flare analysis and annualized severe SFI flare rate analysis as major secondary and secondary endpoints, respectively.
- Removed the time to first mild/moderate flare analysis because the analysis treats patients with severe flares as being the same as patients with no flares.
- Added the other secondary objectives from protocol to [Table JAIA.4.1](#).
- Added randomized and per protocol populations in the analysis populations.
- Added clarification of the definition of baseline and postbaseline.
- Added the definition of intercurrent events.
- Updated the order of covariance structure for mixed model for repeated measures (MMRM) analysis.
- Removed pattern mixture model for handling missing data.
- Added hybrid imputation (MI) for handling missing data due to COVID-19.
- Updated the figure for graphical testing scheme.
- Added the summary of pre-existing conditions in the patient characteristics section.
- Updated the treatment compliance criteria.
- Updated the protocol-specified concomitant medication rules and clarified the definition of baseline concomitant medication.
- Modified the derivation of efficacy/health outcomes measures and endpoints including the missing imputation approach.
- Added organ domain improvement/worsening defined by SLEDAI-2K (SLEDAI 2000) and British Isles Lupus Assessment Group (BILAG), Systemic Lupus Erythematosus Responder Index (SRI)-4 components, BICLA (British Isles Lupus Assessment Group), BICLA components, time to first severe SFI flare, and discontinuation of corticosteroid in the derivation of efficacy/health outcomes measures and endpoints.
- Added Per Protocol, COVID free (PPCV), Per Protocol (PP), and As Collected (AC) datapoint sets for efficacy/health outcomes analyses.
- Added analysis on PPCV and AC datapoint sets for BICLA responder and time to first severe flare analysis in modified intent-to-treat (mITT) population.
- Added analysis on PPCV datapoint sets with hybrid imputation for SRI-4 in per protocol population, and for each component of SRI-4 and BICLA in mITT population.
- Added analysis on PP datapoint sets for organ domain improvement/worsening defined by SLEDAI-2K and BILAG, and for change from baseline of Systemic Lupus International Collaborating Clinics/American College of Rheumatology Damage Index (SLICC/ACR) damage score.

- Added analysis on PP and PPCV datapoint sets for additional corticosteroid sparing endpoints.
- Modified tipping point analysis to provide 2-dimensional results along with a modified analysis framework.
- Added exposure adjusted analyses for adverse events.
- Added the summary of treatment-emergent potential hepatic disorders based on Medical Dictionary for Regulatory Activities (MedDRA) Standardized MedDRA Queries (SMQs).
- Removed the analysis of Framingham risk score.
- Added subgroup analysis section for SRI-4 responder rate at the Week 52 visit by demographic and clinical characteristic subgroups.
- Modified the analyses of adverse events and treatment-emergent lab tests and vital signs by defining the follow-up data as all data occurring up to and including 30 days after last dose of treatment.
- Added the summaries and listings of patients with COVID-19 impact.
- Updated the anatomical therapeutic chemical (ATC) codes and medical review process of prohibited medication in [Appendix 1](#).
- Moved the table of patient characteristics to [Appendix 2](#), and updated a few categories.
- Added [Appendix 3](#) of Efficacy Laboratory Analytes.
- Revised the detailed instructions for calculating joint assessment scores and added to [Appendix 4](#).
- Added SFI severe flare identification in [Appendix 5](#).
- Removed publicly available efficacy scale derivations from appendix.
- Made other minor typographical corrections and clarifications not affecting content.

4 Study Objectives

Table JAIA.4.1 provides the protocol defined primary and major secondary objectives and endpoints of the study. Additional secondary endpoints to provide supportive evidence of efficacy are described in Table JAIA.6.6.

The estimand (ICH E9 R1) associated with each endpoint/analysis is documented in the following places:

- The population of interest is described in the protocol inclusion/exclusion criteria and in this document in Table JAIA.6.1 and Section 6.2. The endpoints/variables may be found in Table JAIA.6.4 and Table JAIA.6.6.
- The handling of intercurrent events and missing data may be found in Section 6.4.2 and Table JAIA.6.5.
- Population summary measures are described in Table JAIA.6.6.

Table JAIA.4.1. Primary and Major Secondary Objectives and Endpoints

Objectives	Endpoints (Variables) ^a
Primary^b	
To evaluate the effect of baricitinib 4-mg QD and background SoC therapy compared to placebo and SoC on SLE disease activity	
 • Proportion of patients achieving an SRI-4 response at Week 52, defined as: 
 • a reduction of ≥ 4 points from baseline in SLEDAI-2K score, and • No new BILAG A and no more than 1 new BILAG B disease activity score, and • No worsening (defined as an increase of ≥ 0.3 points [10 mm] from baseline) in the PGA of Disease Activity.
Major Secondary^c	
To evaluate the effect of baricitinib 4-mg QD plus SoC compared to placebo plus SoC on SLE disease activity	
 • Proportion of patients achieving an SRI-4 response at Week 24 • Proportion of patients achieving a LLDAS response at Week 52
To evaluate the corticosteroid sparing effect of baricitinib 4-mg QD plus SoC compared to placebo plus SoC	
 • Proportion of patients receiving >7.5 mg prednisone (or equivalent) at baseline able to decrease dose by $\geq 25\%$ to a prednisone equivalent dose of ≤ 7.5 mg/day maintained between Week 40 and Week 52
To evaluate the effect of baricitinib 4-mg QD plus SoC compared to placebo plus SoC on SLE flares	
 • Time to first severe flare over 52 weeks
To evaluate the effect of baricitinib 4-mg QD plus SoC compared to placebo plus SoC on PROs	
 • Change from baseline in Worst Pain NRS at Week 52 • Change from baseline in FACIT-Fatigue total score at Week 52

Primary and Major Secondary Objectives and Endpoints

Objectives	Endpoints (Variables)^a
To evaluate the effect of baricitinib 2-mg QD plus SoC compared to placebo plus SoC on SLE disease activity	
 • Proportion of patients achieving an SRI-4 response at Week 52 • Proportion of patients achieving an SRI-4 response at Week 24 • Proportion of patients achieving a LLDAS response at Week 52
To evaluate the corticosteroid sparing effect of baricitinib 2-mg QD plus SoC compared to placebo plus SoC	
 • Proportion of patients receiving >7.5 mg prednisone (or equivalent) at baseline able to decrease dose by $\geq 25\%$ to a prednisone equivalent dose of ≤ 7.5 mg/day maintained between Week 40 and Week 52
To evaluate the effect of baricitinib 2-mg QD plus SoC compared to placebo plus SoC on SLE flares	
 • Time to first severe flare over 52 weeks
To evaluate the effect of baricitinib 2-mg QD plus SoC compared to placebo plus SoC on PROs	
 • Change from baseline in Worst Pain NRS at Week 52 • Change from baseline in FACIT-Fatigue total score at Week 52
Other Secondary (Non-Multiplicity Controlled)	
To evaluate the effect of baricitinib 4-mg or 2-mg QD plus SoC compared to placebo plus SoC on SLE disease activity	
 • Change from baseline in total SLEDAI-2K scores over time through Week 52 • Change from baseline in PGA score over time through Week 52 • Proportion of patients achieving an SRI-4 response over time through Week 52 • Proportion of patients achieving an SRI-5, -6, -7, and -8 response over time through Week 52. • Proportion of patients achieving reduction of ≥ 4 points from baseline in SLEDAI-2K score at Week 52 • Proportion of patients with no new BILAG A and no more than 1 new BILAG B disease activity score at Week 52 • Proportion of patients with no worsening (defined as an increase of ≥ 0.3 points [10 mm] from baseline) in the PGA of Disease Activity at Week 52 • Proportion of patients achieving a BICLA response at Week 52, defined as: 
 • Reduction of all baseline BILAG A to B/C/D and baseline BILAG B to C/D, and no BILAG worsening in other organ systems, where worsening is defined as ≥ 1 new BILAG A or ≥ 2 new BILAG B • No worsening from baseline in SLEDAI-2K, where worsening is defined as an increase from baseline of >0 points in SLEDAI-2K • No worsening from baseline in participants' lupus disease activity, where worsening is defined by an increase ≥ 0.30 points on a 3-point PGA VAS

Primary and Major Secondary Objectives and Endpoints

Objectives	Endpoints (Variables) ^a
To evaluate the corticosteroid sparing effect of baricitinib 4-mg or 2-mg QD plus SoC compared to placebo plus SoC	
 Change from baseline in prednisone dose at Week 52 Proportion of patients taking corticosteroids at baseline able to discontinue use at Week 52
To evaluate the effect of baricitinib 4-mg or 2-mg QD plus SoC compared to placebo plus SoC on SLE flares	
 Time to first mild/moderate flare over 52 weeks* Time to first flare (any severity) over 52 weeks Annualized mild/moderate flare rate Annualized severe flare rate Annualized flare rate (any severity)
To evaluate the effect of baricitinib 4-mg QD or 2-mg QD plus SoC compared to placebo plus SoC on mucocutaneous manifestations of SLE	
 Proportion of patients with CLASI total activity score ≥ 10 at baseline with $\geq 50\%$ reduction in CLASI total activity score at Week 52
To evaluate the effect of baricitinib 4-mg QD or 2-mg QD plus SoC compared to placebo plus SoC on musculoskeletal manifestations of SLE	
 Change from baseline in tender joint count at Week 52 Change from baseline in swollen joint count at Week 52
To evaluate the effect of baricitinib 4-mg QD or 2-mg QD plus SoC compared to placebo plus SoC on individual organ system disease activity	
 Proportion of patients with improvement in each SLEDAI-2K organ system versus baseline at Week 52 Proportion of patients with worsening in each SLEDAI-2K organ system versus baseline at Week 52
To evaluate the effect of baricitinib 4-mg QD or 2-mg QD plus SoC compared to placebo plus SoC on PROs	
 Change from baseline in Worst Fatigue NRS at Week 52 Change from baseline in Worst Joint Pain NRS at Week 52 Change from baseline in Joint Stiffness Duration at Week 52 Change from baseline in Joint Stiffness Severity NRS at Week 52 Change from baseline in Patient Global Impression of Severity at Week 52 Change from baseline in Patient Global Impression of Change at Week 52 Change from baseline in mental component score (MCS), physical component score (PCS), and domain scores in the Short-Form 36-item health survey version 2 (SF-36v2) acute at Week 52 Change from baseline in the EQ-5D-5L at Week 52 Change from baseline in the WPAI-Lupus at Week 52

Primary and Major Secondary Objectives and Endpoints

Objectives	Endpoints (Variables) ^a
To measure baricitinib PK exposure and assess the relationship between exposure and efficacy	
 Population pharmacokinetics of baricitinib in patients with SLE Proportions of patients achieving SRI-4 by exposure quartile

Abbreviations: BILAG = British Isles Lupus Assessment Group; BICLA = British Isles Lupus Assessment Group Based Composite Lupus Assessment; CLASI = Cutaneous Lupus Erythematosus Disease Area and Severity Index; EQ-5D-5L = 5-level EQ-5D version; FACIT = Functional Assessment of Chronic Illness Therapy; LLDAS= Lupus Low Disease Activity State; MCS = mental component score; NRS = numeric rating scale; PGA = Physician Global Assessment; PK = pharmacokinetics; PRO = patient-reported outcome; QD = once daily; SF-36v2 = Short-Form 36-item health survey version 2; SLE = systemic lupus erythematosus; SLEDAI-2K = Systemic Lupus Erythematosus Disease Activity Index 2000; SoC = standard of care; SRI = Systemic Lupus Erythematosus Responder Index; VAS = visual analogue scale; WPAI-Lupus = Work Productivity and Activity Impairment Lupus.

- ^a Additional analyses for other secondary (non-multiplicity controlled) endpoints are included in [Table JAIA.6.6](#).
- b All primary and major secondary endpoint analyses will utilize a multiplicity control approach based on a graphical multiple testing procedure to control the overall family-wise type I error rate at a 2-sided alpha level of 0.05. The graphical multiple testing procedure described in Bretz et al. 2009 will be used.
- c The order of testing of the major secondary endpoints is determined from the results of statistical simulations before study team is unblinded to efficacy results.
- * This objective is written as it is in protocol amendment (b), but will be removed because the analysis treats patients with severe flares as being the same as patients with no flares.

5 Study Design

5.1 Summary of Study Design

Study I4V-MC-JAIA (JAIA) is a Phase 3, multicenter, randomized, double-blind, parallel-group, placebo-controlled, outpatient, 52-week study evaluating the efficacy and safety of baricitinib 4-mg and 2-mg in patients with systemic lupus erythematosus (SLE) receiving standard therapy. The study has a screening period followed by a 52-week double-blinded treatment period and a 4-week post-treatment follow-up period.

Patients will be randomized in a 1:1:1 ratio between baricitinib 4-mg, 2-mg, and placebo. Study treatment will be administered as 2-mg and 4-mg tablets once daily (QD). Patients with documented renal impairment (defined as screening estimated glomerular filtration rate [eGFR] ≥ 40 to < 60 mL/min/1.73 m²), who are randomized to active treatment (either to the baricitinib 4-mg arm or the baricitinib 2-mg arm) will receive a baricitinib 2-mg QD dose by the interactive web-response system (IWRS).

Investigators are encouraged to taper corticosteroids according to clinical practice with a goal of ≤ 7.5 mg/day by Week 40. A single corticosteroid burst is permitted for patients with increased disease activity early in the treatment period. Complete details of corticosteroid rules in relation to the clinical trial endpoints can be found in JAIA Protocol (b) Section 7.7.1.

Patients who were unable to attend Visit 16 within the original protocol-defined window (Week 52/Day 365 \pm 4 days) due to COVID-19 were permitted to delay completion of the Visit 16 by up to 1 month. Patients who complete treatment in this study through Visit 16 may be eligible to participate in a study extension, if enrollment criteria are met.

[figure not shown]

Figure JAIA.5.1.

Illustrates the study design.

5.2 Determination of Sample Size

Study JAIA will randomize approximately 750 patients with a 1:1:1 ratio between baricitinib 4-mg, 2-mg, and placebo. The proposed sample size will ensure >90% power to detect an absolute difference of 17% between a baricitinib treatment group and the placebo treatment group assuming a 40% placebo response rate for the primary endpoint using a 2-sided α of 0.05. The anticipated effect size represents a clinically relevant difference.

Sample size and power estimates were obtained from nQuery® Advisor 7.0 using the χ^2 test of equal proportions.

5.3 Method of Assignment to Treatment

Patients who meet all criteria for enrollment will be randomized in a 1:1:1 ratio (baricitinib 4-mg; baricitinib 2-mg; placebo) to double-blind treatment at Visit 2 (Week 0). Randomization will be stratified by disease activity (total Systemic Lupus Erythematosus Disease Activity Index 2000 [SLEDAI-2K] <10; \geq 10), corticosteroid dose (<10 mg/day; \geq 10 mg/day prednisone or equivalent at baseline), and region as given in [Table JAIA.5.1](#).

Assignment to treatment groups will be determined by a computer-generated random sequence using an IWRS. The IWRS will be used to assign packages containing double-blind investigational product to each patient, starting at Visit 2 (Week 0), and at each visit subsequent through Visit 15 (Week 48).

Table JAIA.5.1. Countries and Associated Geographical Regions

Geographical Region	Country or Countries
North America	United States
Central, South America and Mexico	Argentina, Chile, Colombia
Europe	France, Italy, Poland, Romania, Spain
Asia	Japan, Korea, Philippines
Rest of World	India, Serbia, South Africa

6 A Priori Statistical Methods

6.1 General Considerations

This SAP is intended to describe the analyses of all primary and secondary objectives, as well as safety assessments, for Study JAIA. Sensitivity and supplementary analyses intended to support the primary and major secondary analyses are also included. Exploratory analyses will be described in a separate document.

Statistical analysis of this study will be the responsibility of Eli Lilly and Company (Lilly) or its designee.

Not all displays described in this SAP will necessarily be included in the clinical study report (CSR). Not all displays will necessarily be created as a “static” display. Some may be incorporated into interactive display tools such as Spotfire instead of, or in addition to, a static display. Any display described in this SAP and not included in the CSR would be available upon request.

Throughout this document when analyses for corticosteroids are described, only systemic corticosteroids specified in [Appendix 1](#) are intended for inclusion, unless otherwise specified. In addition, unless otherwise specified, accommodations for COVID-19 in analyses, summaries, and listings are specific to non-COVID-19-infection-related events.

6.2 Definition of Populations

Analysis populations are defined in [Table JAIA.6.1](#) along with their associated purpose. The treatment groups and inferential comparisons described in this table will be used unless otherwise specified. Also, unless otherwise specified patients will be analyzed according to the treatment to which they were assigned.

Table JAIA.6.1. Analysis Populations

Population	Description
Screened Population	
Definition: Includes all patients who signed informed consent form.
 
Purpose: Used for summarizing screen failures and reason for screen failures.
 
Treatment Groups: None
 
Inferential Comparisons: None

Randomized Population	
Definition: Includes all randomized patients.
 
Purpose: Used for listing patient disposition and treatment assignment.
 
Treatment Groups: baricitinib 2-mg QD, baricitinib 4-mg QD, placebo QD
 
Inferential Comparisons: None

mITT Population	
Definition: All randomized patients who receive at least 1 dose of study treatment (regardless of if the patient does not receive the correct treatment, or otherwise does not follow the protocol).
 
Purpose: Used for efficacy and health outcomes related analyses.
 
Treatment Groups: baricitinib 2-mg QD, baricitinib 4-mg QD, placebo QD
 
Inferential Comparisons: baricitinib 4-mg QD vs. placebo QD; baricitinib 2-mg QD vs. placebo QD

Per Protocol Population	
Definition: All randomized patients who received at least 1 dose of study treatment without important protocol deviations that impacted the analysis (defined in a separate study deviation rules document).
 
Purpose: Used for the sensitivity analysis for the primary efficacy.
 
Treatment Groups: baricitinib 2-mg QD, baricitinib 4-mg QD, placebo QD
 
Inferential Comparisons: baricitinib 4-mg QD vs. placebo QD; baricitinib 2-mg QD vs. placebo QD

Safety Population	
Definition: The safety population is defined as all randomized patients who receive at least 1 dose of investigational product and who did not discontinue from the study for the reason “Lost to follow-up” at the first postbaseline visit.
 
Purpose: Used for all safety analyses.
 
Treatment Groups: baricitinib 2-mg QD, baricitinib 4-mg QD, placebo QD
 
Inferential Comparisons: baricitinib 4-mg QD vs. placebo QD; baricitinib 2-mg QD vs. placebo QD

Abbreviations: mITT = modified intent-to-treat; QD = once daily.

Patients who are randomized to 4 mg, but who have decreased renal function, identified by an eGFR measurement of <60 mL/min/1.73m² at screening, will receive a dose of 2 mg QD. These patients will be summarized within the 4-mg treatment arm for all summaries unless otherwise noted. A list of these patients who had this dose adjustment will be provided. A list of patients who had a dose correction due to incorrect eGFR entry at randomization will also be provided.

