Protocol-defined visit windows are defined as ± 3 days for Visit 3 (Week 1) and ± 4 days, from Visit 4 (Week 4) until Visit 16 (Week 52). If there is data within the protocol-defined window, that data will be used in by-visit analyses. If a protocol-defined visit is missing, then the nearest unscheduled visit data that exists will be mapped to that visit and included in by-visit analyses. If 2 unscheduled visits are equidistant to a missing visit, the earlier unscheduled visit will be used.

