6.13 Safety Analyses

The definition of baseline and post-baseline are described in Section 6.3.

Safety analyses will include data from first dose of the study treatment and patients will be analyzed according to the investigational product which they were randomized at Week 0 (Visit 2). Safety analyses will use the safety population defined in [Table JAIA.6.1](#).

Safety topics that will be addressed include the following: AEs including TEAEs and SAEs, clinical laboratory evaluations, vital signs and physical characteristics, Columbia Suicide Severity Rating Scale (C-SSRS), the Self-Harm Supplemental Form, Quick Inventory of Depressive Symptomatology Self Report (QIDS-SR16), and safety in special groups and circumstances, including adverse events of special interest and investigational product interruptions.

For tables that summarize events (such as AEs, categorical lab abnormalities, shift to maximum severity), post-last dose follow-up data will be included. Follow-up data is defined as all data occurring up to and including 30 days after last dose of treatment. In general, for laboratory analytes and vital signs, planned (scheduled visits) and unplanned (unscheduled visits) measures are used for categorical analyses and planned (scheduled visits) measures are used for continuous by-visit analyses including change from last baseline to last postbaseline.

The planned safety analyses are consistent with compound level safety standards that are based on multiple sources, including company standards, internal and external subject matter experts,

and cross-industry initiatives (e.g., white papers produced by a PhUSE Computational Science Working Group [a collaboration with FDA and PhUSE], published in the PhUSE Deliverables Catalog at <https://www.phuse.eu/white-papers>). Descriptions of the safety analyses are provided in this SAP, however, additional details (such as handling of unscheduled visits, missing data, etc.) are in compound level safety standards.

The following statistical methods will be used for safety unless otherwise noted:

- Fisher's exact test will be used for treatment comparisons of proportions, and odds ratios with corresponding 95% CIs, where specified.
- Treatment differences in mean change for continuous measurements will be assessed using an ANCOVA model fitting "baseline" as a covariate. Type 3 sums of squares will be used.

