6.13.2 Adverse Events

Adverse events are recorded in the eCRFs. Each AE will be coded to SOC and PT using the MedDRA version 24.0. Severity of AEs is recorded as mild, moderate, or severe.

A treatment-emergent adverse event (TEAE) is defined as an event that either first occurred or worsened in severity after the first dose of study treatment during the analysis period. The analysis period is defined as the treatment period plus up to 30 days off-drug follow-up time. Refer to the compound-level safety standards for more details.

In general, baseline measurements are those taken prior to starting study medication. Measurements taken during the treatment period are those taken after starting study medication, unless otherwise noted. If study drug is temporarily interrupted and subsequently restarted during the treatment period, the measurements taken during the temporary interruption will be included in the analysis. Where applicable, the time elapsed during the temporary interruption will also be included in analyses.

For events that are gender-specific (as defined by the MedDRA), the denominator and computation of the percentage will include only patients from the given sex.

Planned summaries are specified below and are described more fully in compound level safety standards and in the AE-related PhUSE white paper (Analysis and Displays Associated with Adverse Events: Focus on Adverse Events in Phase 2-4 Clinical Trials and Integrated Summary Document [PhUSE 2017]), available at <https://www.phuse.eu/white-papers>. All analyses will be conducted on the Safety Population.

Table JAIA.6.7. Summary Tables Related to Adverse Events

Analysis
An overview table, with the number and percentage of patients in the safety set with death, a SAE, any TEAE, discontinuation from the study due to an AE, permanent discontinuation from study drug due to an AE, or a severe TEAE
The number and percentage of patients with TEAEs using MedDRA PT nested within SOC
The number and percentage of patients with TEAEs using MedDRA PT (without regard to SOC)
The number and percentage of patients with TEAEs by maximum severity using MedDRA PT
The number and percentage of patients who experienced a serious adverse event (including deaths) using MedDRA PT nested within SOC

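### The safety population drops dosed patients lost to follow-up at the first postbaseline visit, even if they have a recorded post-dose event

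*SAP*

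**What the plan says.** Table JAIA.6.1 (SAP Section 6.2) builds the safety population in two steps. The first is inclusion by dosing: "The safety population is defined as all randomized patients who receive at least 1 dose of investigational product". The second removes some of those patients again, because it keeps only those "who did not discontinue from the study for the reason" of loss to follow-up at the first postbaseline visit.

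The same table gives the purpose of the set: "Used for all safety analyses". Section 6.13 repeats this ("Safety analyses will use the safety population defined in" Table JAIA.6.1), and so does Section 6.13.2: "All analyses will be conducted on the Safety Population". The SAP plans no supportive safety summary on all dosed patients.

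The mITT population in the same table has no such clause. It takes "All randomized patients who receive at least 1 dose of study treatment", whatever happens afterwards.

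**The concern.** Membership of the safety set depends on something that happens after dosing. Randomization does not protect a selection of that kind, and it can differ between arms.

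The clause also looks at the wrong thing. It is triggered by a disposition code, whereas the problem it presumably addresses is the absence of post-dose information. Under Section 6.3 postbaseline data collection begins after the first dose, and under Section 6.13.2 an event can be treatment-emergent from that moment. A patient can therefore have an event on record, later be coded as lost to follow-up at Week 1, and leave the safety set together with the event.

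What is at stake is the count of rare events: MACE, venous thromboembolism, serious or opportunistic infection. For common events the effect is negligible.

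**Working it through.** **No figure of the plan's own.** The SAP does not say how many patients the clause would remove, so there is nothing to reproduce. The check compares the definitions and then sizes the effect under stated assumptions.

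**Who is in which set**

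| Patient | mITT | Safety population |
|---|---|---|
| Dosed, seen at Week 1 | in | in |
| Dosed, discontinued at Week 1 for an adverse event | in | in |
| Dosed, lost to follow-up at Week 1, no event recorded | in | out |
| Dosed, lost to follow-up at Week 1, event recorded | in | out |

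The last row is the defect. The third row is the case for which the clause has a rationale.

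**Inputs**
- About 750 patients randomized 1:1:1 (Section 5.2): 750 / 3 = 250 per arm.
- First postbaseline visit: Visit 3, Week 1, window of 3 days either side (Section 6.3), so at most about 7 + 3 = 10 days after first dose.
- Number removed: not given. Two assumed ranges are 0 to 5 patients in the whole trial, or 0.5% to 3% per arm. The second gives 250 × 0.005 = 1.25 to 250 × 0.03 = 7.5 per arm, or 3.75 to 22.5 in total.

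**Size of one excluded event**
- As a share of an arm: 1 / 250 = 0.4 percentage points.
- Example with assumed counts: 6/250 = 2.40%. Removing one patient with an event gives 5/249 = 2.01%, a change of 0.39 points.

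**Size of adding event-free patients back**
- 5/247 = 2.02% becomes 5/250 = 2.00%, a dilution of 0.02 points for three patients.
- Each adds about 10 / 365.25 = 0.03 patient-years up to the visit, or 40 / 365.25 = 0.11 if the full 30 days of off-drug follow-up in Section 6.13 are counted.

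**Effect on a comparison** (two-sided Fisher's exact test; all counts assumed; placebo 0/250)

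| Active arm | Rate | p |
|---|---|---|
| 6/250, nobody removed | 2.40% | 0.030 |
| 5/247, three removed, one with an event | 2.02% | 0.030 |
| 4/247, three removed, two with events | 1.62% | 0.060 |

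The p-value moves noticeably only if two of the three removed patients had events. Section 6.13 treats safety p-values mainly as flags, so the point rests on the definition and not on this table.

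**The case against.** The strongest defence is that a patient lost at Week 1 has usually supplied little or no post-dose information. The main safety tables are crude percentages compared by Fisher's exact test, and in those tables an unobserved patient counts as event-free. Leaving such patients out avoids that slight understatement. Exposure-adjusted rates do not remove the difficulty entirely, because a lost patient may lack a last-dose date, and Section 6.13.1 refers its imputation to the compound-level standards. This stands as a reason for the clause and as a cost of deleting it. It does not justify removing a patient who has a recorded event.

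The route to harm is also narrow. Only one disposition reason triggers the clause. A patient known to have left because of an adverse event would be expected to carry that reason and stay in the set. Nothing in the SAP shows that an affected patient exists. This stands too, and it limits the severity.

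Three stronger readings are tempting, and the document does not support them.
- A reader might infer that the clause contradicts Section 6.13, which says "Safety analyses will include data from first dose of the study treatment". That sentence sets the data window, and the same paragraph names Table JAIA.6.1 for the patients. The sections agree with each other.
- A reader might infer that these patients vanish from every safety output. Section 6.13.3 plans a listing of deaths whenever they occurred in the study, although it does not name the population. Section 6.7 summarizes disposition on mITT and lists it for all randomized patients. Section 6.19 plans registry summaries of serious events without naming a population. None of these puts the patients back into the adverse event tables.
- A reader might infer that different efficacy and safety denominators are a fault in themselves. The table gives each population its own purpose, so the difference alone is not an error.

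Finally, the definition may be shared across studies through the compound-level standards that Section 6.13 cites. Those are not at hand, so this cannot be judged. It bears on how to make the change, not on whether the clause can drop a recorded event.

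**Conclusion.** The point holds as a low-severity, cheap improvement. As written, the clause selects on a post-dose disposition and can take exposed patients and their recorded events out of the adverse event, serious adverse event, special-interest and exposure-adjusted summaries.

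The size cannot be fixed from the SAP. With about 250 patients per arm, each excluded event is worth about 0.4 percentage points. The number of patients affected is an assumption throughout, probably small because the first postbaseline visit is at Week 1, and possibly zero. There is no basis for saying that the clause favours one arm, only that nothing in it prevents this.

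**What to change.** Define the safety population as all randomized patients who received at least 1 dose, and delete the lost-to-follow-up clause. The safety and mITT populations would then contain the same patients. The SAP already has means of handling short follow-up: Section 6.13 censors event-free patients at the end of the analysis period in the exposure-adjusted rates, and the laboratory-threshold rows of Table JAIA.6.11 count only patients with a postbaseline value.

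The cost is one deleted clause. A few patients with little or no observed follow-up would enter the crude denominators as event-free, lowering percentages very slightly. A footnote is needed if the integrated safety standard keeps the older definition.

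If that standard must be kept here as well, three additions meet the concern:
- report the number excluded per arm;
- list any recorded events in those patients;
- add a sensitivity summary of serious adverse events and events of special interest on all dosed patients.

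If the number excluded is zero, a sentence saying so is enough.
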